8 TREATMENT INTERVENTIONS

8.1 Interventions

Participants will be randomly assigned to one of four treatment groups: 1) peripheral treatment in the form of 5% lidocaine/0.5mg/ml 0.07% estradiol compound cream + placebo pill, 2) centrally-targeted treatment in the form of placebo cream + nortriptyline oral pill (up to 50 mg or highest tolerated dose), 3) combined treatment in the form of 5% lidocaine/0.5mg/ml 0.07% estradiol compound cream + nortriptyline; and 4) placebo cream + placebo pill.

Lidocaine/estradiol cream targets peripheral nerves and tissues affected in VBD; the comparison treatment will be an identical-appearing placebo Moisturel™ cream. Participants will be provided with a diagram and written instructions (see **Appendix B**), detailing how to apply the cream to the vaginal vestibule daily for weeks 1-16. Treatment with lidocaine/estradiol or placebo cream will be terminated at 16 weeks.

Nortriptyline is a centrally-acting tricyclic antidepressant that is FDA-approved for treatment of neuropathic pain. Dosing will begin with one 10 mg pill nightly for week 1, then two 10 mg pills nightly for week 2, three 10 mg pills nightly for week 3, four 10 mg pills nightly for week 4, and five for weeks 5 -16. In the event of side-effects without significant adverse events, participants will be advised to decrease dosage by one pill weekly until a tolerable dose is achieved. Treatment with nortriptyline or placebo pill will be tapered off over weeks 16-18, decreasing the dose by 10 mg every 4 days. Participants will be provided with a list of drugs to avoid that are known to interact with nortriptyline (see **Appendix C**).

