8.3 Drug Dispensing

Identical-appearing creams and pills will be packaged and distributed by Central Compounding Pharmacy to the UNC site, and by the Pacifica Compounding Pharmacy to the UCLA site. At the baseline visit, participants will receive a sufficient supply of study drug for weeks 1-8, and some (3 days) extra in the event of delay in scheduling visit 2. At the 8-week visit, participants will receive a sufficient supply of study drug for the remaining weeks 9-16, and some (3 days) extra in the event of delay in scheduling visit 3. Patients will be instructed to take the medication as required by the protocol.

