8.5 Drug Accountability

Participants are instructed to return all used, partly used and unused trial products (study drugs and packaging material) at each study visit. Returned trial product(s) must be stored separately from the non-allocated trial product(s) until drug accountability has been reconciled. The respective clinical investigators will be responsible for monitoring all received, used, partly used and unused trial product(s).

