11 FOLLOW-UP EVALUATIONS

11.1 Visit 2 (8-Week)

Upon arrival, participants will return any remaining study medication to the research team.

The week 8 visit procedures and assessments will be performed in the following order:

- Tampon test with 0-10 NRS
- Blood collection and processing
- Participant questionnaires:

- VPAQ
- PROMIS BPSFS-F
- COPC follow-up survey
- SF12v2
- SCL-27
- PILL
- PSS
- Sleep scale
- Remote bodily PPTs (deltoid, shin, trapezius)
- Qualitative pelvic sensory testing
- Vaginal sample collection
- Local vestibular PPTs (5, 6, and 7 o'clock)

At the end of visit 2, participants will receive a sufficient supply of study drug for weeks 9-16. Patients will be instructed to take the medication as required by the protocol and complete a daily medication diary.

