11.2 Visit 3 (16-Week)

Upon arrival, participants will return any remaining study medication to the research team. Study medication will be discontinued.

The week 16 visit procedures and assessments will be performed in the following order:

- Tampon test with 0-10 NRS
- Blood collection and processing
- Participant questionnaires:
 - VPAQ
 - PROMIS BPSFS-F
 - COPC follow-up survey
 - SF12v2
 - SCL-27
 - PILL
 - PSS
 - Sleep scale
- Remote bodily PPTs (deltoid, shin, trapezius)
- Qualitative pelvic sensory testing
- Vaginal sample collection
- Local vestibular PPTs (5, 6, and 7 o'clock)

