11.3 Visit 4 (24-Week)

The week 24 visit procedures and assessments will be performed in the following order:

- Tampon test with 0-10 NRS
- Blood collection and processing
- Participant questionnaires:
 - VPAQ
 - PROMIS BPSFS-F
 - COPC follow-up survey
 - SF12v2
 - SCL-27
 - PILL
 - PSS
 - Sleep scale
- Remote bodily PPTs (deltoid, shin, trapezius)

- Qualitative pelvic sensory testing
- Vaginal sample collection
- Local vestibular PPTs (5, 6, and 7 o'clock)

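### Section 8.1 orders a pill taper after week 16 that the week-16 visit procedures cancel and no visible section supplies; separately, sections 8.2 and 8.9 conflict on SSRIs and SNRIs

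*Combined protocol and SAP*

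**What the plan says.** **Stopping treatment.** Section 8.1 handles the two products differently. For the cream: "Treatment with lidocaine/estradiol or placebo cream will be terminated at 16 weeks". For the pill: "Treatment with nortriptyline or placebo pill will be tapered off over weeks 16-18, decreasing the dose by 10 mg every 4 days". The pill dose at that time is five 10 mg pills nightly, or fewer if side effects have forced a reduction.

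Section 11.2 makes no such distinction. On arrival at visit 3, "participants will return any remaining study medication to the research team. Study medication will be discontinued". Section 8.5 is consistent with that: "Participants are instructed to return all used, partly used and unused trial products (study drugs and packaging material) at each study visit".

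**Supply.** The last dispensing is at visit 2. Section 8.3 says "participants will receive a sufficient supply of study drug for the remaining weeks 9-16, and some (3 days) extra", and ties the extra days to a delay in visit 3. Section 11.1 says only "At the end of visit 2, participants will receive a sufficient supply of study drug for weeks 9-16". Section 11.2 lists no dispensing. Appendix A marks medication compliance at weeks 8 and 16, not at week 24.

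**Antidepressants.** Section 8.9 bars SSRIs and SNRIs for the whole study, to be confirmed at each follow-up visit. Section 8.2 sends a potential participant who takes citalopram or escitalopram, or two or more serotonergic antidepressants, to a consult between the study physician and her prescriber on whether nortriptyline is safe for her in this trial. It also plans contact within 24 hours of each start or increase for randomized participants on other serotonergic antidepressants. The washout list in 7.3 criterion 1 is open-ended and names neither class. Appendix C lists both as interacting drugs.

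**The concern.** The protocol orders a precaution and then gives visit instructions under which it cannot be carried out. Site staff work from the visit procedures, and these end the pill in one step at up to 50 mg.

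It also leaves time off drug undefined in a planned secondary analysis. Section 15.2 examines change from week 16 to week 24 and predicts that the two subtypes will respond differently to withdrawal. Whether the pill stopped on day 112 or about two weeks later is part of that exposure.

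On antidepressants, the same woman can be cleared under 8.2 and be a protocol violation under 8.9. Section 8.2 itself names serotonin syndrome and QT prolongation as the risks. Section 3.2 counts SSRIs among the centrally acting drugs that relieved pain in VBD-c, so they also bear on the question under study.

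**Working it through.** The plan gives no pill count for the taper, so there is no figure to reproduce. The check compares the sections and counts pills and days.

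**Inputs.** Dose n = 5 pills nightly or fewer, in 10 mg steps every 4 days (8.1). Supply to day 112 + 3 = 115 (8.3). Visits on days 56, 112 and 168, each +/- 5 days (Appendix A).

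**1. What the taper needs.** If the first reduction is made at once, it lasts 4(n-1) days and uses 2n(n-1) pills. The last pill day is 112 + 4(n-1), and time off drug at the nominal week-24 visit is 168 minus that day.

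| Dose at week 16 | Days | Pills | Last pill day | Days off drug at day 168 |
|---|---|---|---|---|
| 50 mg | 16 | 40 | 128 | 40 |
| 40 mg | 12 | 24 | 124 | 44 |
| 30 mg | 8 | 12 | 120 | 48 |
| 20 mg | 4 | 4 | 116 | 52 |
| 10 mg | 0 | 0 | 112 | 56 |

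For 50 mg this is 4 x (4+3+2+1) = 40 pills. If the starting dose is first held for 4 days, the taper lasts 4n days and uses 2n(n+1) pills: 20 days and 60 pills from 50 mg. After an abrupt stop on day 112, time off drug is 168 - 112 = 56 days at every dose.

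**2. What a woman has in hand at visit 3.** At full dose with supply to day 115, she has 5 x (115 - visit day) pills: 40 on day 107, 15 on day 112, none on day 115. Under 8.5 and 11.2 she hands back whatever is left, and nothing is issued in its place.

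**3. Length against the stated period.** Week 18 ends on day 18 x 7 = 126. The 50 mg taper ends on day 128, 2 days later.

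**4. Spare supply.** The first pack runs to day 56 + 3 = 59 and the visit 2 window to day 61, a gap of 2 days. If the second supply runs to day 115, the gap before the latest visit 3 is 117 - 115 = 2 days. If the second pack is instead a fixed 59 days from a visit 2 on day 51, it ends on day 110 and the gap is 7 days. Raising a fixed pack to 56 + 5 = 61 days would then reach only day 112. Counting the pack to day 117 closes the gap whatever the date of visit 2.

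**5. Antidepressants.** Citalopram and escitalopram are SSRIs, so 8.9 excludes the women for whom 8.2 provides a clearance route. The 24-hour contact in 8.2 refers to women already randomized, so 8.2 cannot be read as covering screening alone. The open wording in 7.3 does not decide between the two.

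**The case against.** The best reply is that 8.1 is the dosing section, 11.2 is a brief visit summary, and participants are told to take the drug as the protocol requires, so a sensible site would follow 8.1. That is probably the intent. But intent does not put pills in the participant's hands after she has returned them.

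Several further points stand and limit the concern:

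- A reader might infer that no woman has enough pills to taper. The documents do not support that. An early visit 3 leaves 40 at full dose, and a reduced dose can leave enough too. The obstacle is the return-and-discontinue instruction together with the lack of any dispensing at visit 3.
- A reader might infer that nothing follows the drug after visit 3. Section 8.5 already requires return at every study visit, which includes week 24, and adverse events are captured through Month 6. Only the compliance item in Appendix A is absent at week 24.
- The 2-day overrun at 50 mg is trivial. Counting weeks 16, 17 and 18 inclusively gives 21 days, and no consequence is attached to the difference.
- Carrying out the taper does not equalize time off drug. It replaces a uniform 56 days with 40 to 56 days by dose.
- The Appendix B handout and most of the Appendix D calendar are not in the text available here. The visible calendar covers the first two months only. The statement about supply is therefore limited to visible text.
- Section 8.2 is detailed and may be the rule the sponsor intends. The share of women on SSRIs or SNRIs is not given, so the recruitment cost of a strict ban is unknown. Deleting the 24-hour contact would remove a safeguard for a woman later found to be taking one of these drugs.

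**Conclusion.** The taper conflict holds and should be fixed. As written, the visit procedures end the pill abruptly from up to 50 mg where 8.1 orders a stepwise reduction, which from 50 mg needs 40 pills over 16 days if the first step is immediate. The day counts assume visits on their nominal dates.

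Two stronger readings are tempting and are not supported. One is that participants will be harmed: no section describes harm from an abrupt stop. The other is that the trial's comparisons are biased: active and placebo pills fall under the same instructions, randomization is stratified by site, and the week-16 assessments come before any taper. What remains is a precaution ordered but not delivered, and an undefined off-drug interval in the secondary comparison of weeks 16 to 24.

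The antidepressant conflict also holds. The documents do not show which rule should prevail, and no effect on the week-16 primary comparison is shown.

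The spare-supply item is minor. It is the only one of the three that could reach the week-16 assessment, through missed doses before a late visit: up to 2 days if supply runs to day 115, and 7 only under the fixed-pack assumption.

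**What to change.** **Taper.** In 11.2 and 8.3, stop only the cream at week 16 and dispense at visit 3 a blinded taper pack matched to the pill allocation, of up to 40 pills. In 8.1, state the taper as 40, 30, 20 and 10 mg for 4 days each, 16 days in all, with lower doses entering at their next step. Add a compliance item at week 24 in Appendix A; pack return at that visit needs no new rule. Record the date of the last pill, so that the 40-to-56-day spread can be described in the analysis of weeks 16 to 24.

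**Antidepressants.** The sponsor should choose either a ban or permitted use after a consult, and write the same rule in 7.3, 8.2, 8.9 and Appendix C. Keep the 24-hour contact under either choice.

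**Spare supply.** Give 5 spare days of cream and pills instead of 3, with the second pack counted to day 117 whatever the date of visit 2. That pack covers 117 - 56 = 61 days from a nominal visit 2 and 117 - 51 = 66 days from the earliest one.

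**Cost.** One protocol amendment with IRB approval, a revised Appendix C handout, at most 400 x 40 = 16,000 taper pills, a few more days of supply, and one added compliance item. No extra visits, and no change to sample size or significance level. The recruitment cost of the antidepressant rule depends on the choice made and cannot be estimated from the documents.

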8.2 Potential Side Effects and Risk Reduction Plan

Expected risks associated with lidocaine/estradiol compound cream include an adverse reaction to either medication or the compounded base. Lidocaine is well tolerated and safe, particularly with topical administration in small doses which significantly reduces the risk of lidocaine toxicity. The proposed daily dose is extremely small, with minimal systemic uptake when used as instructed. As with any medication, participants will be clearly instructed to use as directed. Significant over-usage would be required to approach toxicity. This is extremely rare in clinical practice. The medication will not be used in women with prior sensitivity or allergy to local anesthetics. A mild burning or tingling sensation with application is typical and resolves once the anesthetic takes effect. There is a rare risk of erythema, burning or blistering at the application site. The lidocaine will be compounded in a hydrophilic petrolatum, an inert and well-tolerated compounding cream. The second component of this compounded cream is estradiol. Like the lidocaine, women with prior sensitivity to this medication should not be enrolled, as well as women who have contraindications to topical estrogen therapy. The topical application has very low systemic uptake (0.01% per ½ gram dose), is well-tolerated and safe in reproductive-aged women. Women with potential contraindications to systemic estrogen, such as those with breast cancer, stroke or coronary artery disease, may still receive topical estrogen due to the extremely low absorption rate. In these cases, the treating physician will be contacted for permission to participate in the study, as is the protocol with clinical use of topical estrogen. Participants will be

instructed to notify the research team if they experience any adverse reaction.

Nortriptyline, a second-generation tricyclic antidepressant, with few associated risks is well-tolerated when compared to other agents in this pharmacologic class. The medication will be administered at night to minimize symptoms but it has the effect of insomnia, participants may switch to morning administration. The maximum dose of this medication is 150 mg/day for major depression, but is efficacious at lower doses for the management of pain disorders. This medication should not be used in participants with: homicidal or suicidal ideations, in the acute recovery phase of a myocardial infarction (due to risk of arrhythmia), epilepsy, or acute angle glaucoma. Expected side effects with nortriptyline include drowsiness, difficulty sleeping (insomnia), cloudy thinking, and dry mouth. Other potential side effects include nausea, vomiting, loss of appetite, weight gain/loss, anxiety, hives/rash, delayed micturition, urinary retention, constipation, vision changes, breast swelling, decreased sexual drive, hyper/hypoglycemia, tachycardia or irregular heartbeat. Risk of serotonin syndrome is increased when participants are taking other serotonergic medications in addition to nortriptyline. Risk of long QT syndrome is increased when participants are taking citalopram or escitalopram. If the potential participant endorses either taking two or more serotonergic antidepressant medications or taking either citalopram or escitalopram, then the study MD will consult with the prescribing provider to determine if it would be safe for the potential participant to take nortriptyline in this clinical trial. Since serotonin syndrome is most likely to occur within 24 hours of starting/increasing the dosage of a serotonergic medication, the researcher will attempt to contact randomized participants within 24 hours of starting/increasing nortriptyline doses if the participant is taking other serotonergic antidepressants.

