5.3 Baseline Evaluation Phase and Randomization

Immediately following screening, research participants will complete all baseline assessments, including 1) completion of validated questionnaires to measure perceived pain, health, mood, and sexual function 2) vulvar exam and quantitative sensory testing to measure pressure pain thresholds at local (vaginal) and remote body sites, and 3) collection of biologic samples to measure local (vaginal) and systemic (blood) cytokines and miRNAs. The complete schedule of assessments to be obtained during the baseline visit is outlined in **Appendix A**.

Participants who fulfill all the inclusion criteria and none of the exclusion criteria will be randomly assigned on a 1:1:1:1 ratio to one of four treatment groups:

- 5% lidocaine/0.5mg/ml 0.07% estradiol compound vaginal cream + placebo pill
- placebo vaginal cream + nortriptyline pill
- 5% lidocaine/0.5mg/ml 0.07% estradiol compound vaginal cream + nortriptyline pill
- placebo vaginal cream + placebo pill

Medication assignments will be determined by the Duke Clinical Research Institute (DCRI) using randomized blocks, and then stratified by enrollment site. The DCRI will create a SAS program to generate the random sequence that will be loaded in RedCap. Participants and research personnel will be blinded to medication assignment.

[figure not shown]
During the baseline visit, participants will be counseled on optimal study medication administration. Participants will receive a written description of the study with contact numbers of study staff to present to their usual care provider(s).

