7.3 Exclusion Criteria

1. Participants that will be enrolled in this study must be off medications for 30-90 days, depending on the medication dosage, frequency, duration, and half-life. All concomitant medications will need to be documented at the time of screening so the Principal Investigator and medical doctors at each participating site can determine a conservative window. Medications include, but are not limited to: topical lidocaine, estradiol, or lidocaine/estradiol to the vulvar vestibule, nortriptyline or other TCAs, pregabalin, and gabapentin.
2. Presence of active dermatologic vulvar disease or vaginal infection
3. Untreated atrophic vaginitis (participants may undergo treatment and re-evaluation for enrollment if the condition is resolved)
4. Previous vestibulectomy
5. Pregnant or planning on becoming pregnant during the study period.
6. Within the first six months of the postpartum period.
7. Currently breastfeeding/lactating, or within three months of discontinuing breastfeeding/lactation.
8. Active incarceration
9. Cancer within the past year.
10. Chemotherapy and/or radiation treatment within the past year.
11. Unstable medical condition (e.g., renal impairment, significant hematological disease, cardiovascular disease, hepatic insufficiency, neurological disorder, autoimmune disease, or respiratory illness)
12. Clear inflammatory states (e.g., morbid obesity)
13. Use of immunosuppressant medications
14. History of intolerance to nortriptyline, topical lidocaine, or topical estradiol
15. Contraindications to use of nortriptyline: current use, or use within the past 1-3 months, of MAOIs, some NDRIs, Ethylphenidate (DPH), MDPV (Methylenedioxypyrovalerone), Pipradrol (Meratran), Prolintane (Catovit/ Promotil); recent myocardial infarction, active psychotic or suicidal thoughts, narrow angle closure glaucoma
16. Contraindications to the use of lidocaine or local anesthetics
17. Contraindications to the use of topical estrogen therapy

18. Post-menopausal, defined as no menses for 12 consecutive months or surgical removal of both ovaries. (Hysterectomy is not an exclusion)
19. Have not had Botox of the pelvic floor muscles in the last 12 months, or pelvic nerve blocks in the last three months.
20. Are not currently enrolled or planning to enroll in another clinical trial during the course of this trial.
21. Are not currently receiving pelvic physical therapy

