8.8 Unblinding

Randomization data are kept strictly confidential, accessible only to authorized persons (in this case a member of the DCRI team and the pharmacists), until the time of unblinding. The investigative sites will be given access to the treatment code for their participants for emergency unblinding only by calling the CC. In the rare event of necessary unblinding, the CC Medical Monitor must be contacted to discuss the case. Any suspected study drug-related event should be treated as though the patient received active therapy.

At the end of the study, the assigned treatment arm will be unblinded and disclosed to subjects individually in order to allow subjects to seek further management of vestibulodynia with their gynecologist or primary care physician.

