14.2 Definitions

14.2.1 Adverse Events

An adverse event (AE) is defined as any untoward medical occurrence with the use of a drug in a subject whether or not considered drug or biologic related. An AE can therefore be any unfavorable and unintended sign, symptom, or disease temporarily associated with the use of a pharmaceutical product or biologic.

The study is limiting collection of AEs to focus on potential impacts of the blinded study medication. Only the following AEs will be documented in the electronic Case Report Form (eCRF):

- Swelling
- Burning
- Blistering
- Drowsiness
- Difficulty sleeping (insomnia)
- Cloudy thinking
- Dry mouth
- Nausea
- Vomiting
- Loss of appetite
- Weight gain
- Weight loss
- Anxiety
- Hives
- Rash
- Difficulty urinating
- Constipation
- Vision changes
- Breast swelling
- Decreased sexual drive

- Low blood sugar
- High blood sugar
- Increased heart rate
- Irregular heartbeat
- Suicidal thinking
- Mania
- Agitation
- Hallucinations
- Muscle tremor
- Muscle rigidity
- Seizures
- Bone pain

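### Section 8.2 rules out nortriptyline in epilepsy and homicidal ideation, but the exclusion list that controls randomisation (7.3) names neither, so controlled epilepsy is not clearly excluded

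*Combined protocol and SAP*

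**What the plan says.** Section 8.2 states when nortriptyline is not to be given: "This medication should not be used in participants with: homicidal or suicidal ideations", and the same sentence goes on "in the acute recovery phase of a myocardial infarction (due to risk of arrhythmia), epilepsy, or acute angle glaucoma". That makes five conditions.

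Section 7.3 turns contraindications into entry criteria. Exclusion 15 is the nortriptyline item. After a list of drugs it names "recent myocardial infarction, active psychotic or suicidal thoughts, narrow angle closure glaucoma". Exclusion 11 is a general medical item: "Unstable medical condition (e.g., renal impairment, significant hematological disease, cardiovascular disease, hepatic insufficiency, neurological disorder", with autoimmune and respiratory disease as further examples. Exclusion 1 is a washout rule, under which "All concomitant medications will need to be documented at the time of screening" so that the Principal Investigator and site doctors can set a washout window.

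Section 5.3 gives the test for randomisation: "Participants who fulfill all the inclusion criteria and none of the exclusion criteria will be randomly assigned on a 1:1:1:1 ratio". Under section 8.1, two of the four arms contain nortriptyline, raised in weekly 10 mg steps to 50 mg nightly or the highest tolerated dose.

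On other antidepressants, section 8.9 prohibits SSRIs and SNRIs for the whole study. Section 8.2 provides for a call to the prescriber when a candidate takes citalopram, escitalopram or at least two serotonergic antidepressants. It also provides for an attempted contact within 24 hours of a nortriptyline start or increase for randomised women who are taking other serotonergic antidepressants.

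**The concern.** A contraindication protects participants most reliably when it sits in the list that site staff work through before randomisation. Here the protocol identifies epilepsy as a reason not to give the drug, but the nortriptyline item in that list omits it. Allocation is random and blinded, so a woman who passes 7.3 cannot be kept to the arms without nortriptyline. The later safeguards are dose reduction, adverse event follow-up and emergency code-breaking ("The investigative sites will be given access to the treatment code for their participants for emergency unblinding only by calling the CC"), and they act only once exposure has begun. What is at stake is an avoidable exposure that the sponsor has already judged unsuitable.

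The antidepressant wording is a separate matter. A site following 8.9 would not have randomised women on SSRIs or SNRIs to telephone, whereas a site following 8.2 might.

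**Working it through.** The check is mainly a comparison of text, taking each condition in 8.2 against the 21 exclusions in 7.3.

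1. Suicidal ideation: named in exclusion 15.
2. Acute recovery from myocardial infarction: covered in exclusion 15 as recent infarction.
3. Acute angle glaucoma: covered in exclusion 15 as narrow angle closure glaucoma.
4. Epilepsy: named in no exclusion. Exclusion 11 mentions neurological disorder, but only as an example of an unstable condition. Uncontrolled epilepsy is reached; controlled epilepsy is not clearly reached.
5. Homicidal ideation: named in no exclusion. Exclusion 15 covers active psychotic thoughts, which would take in some cases but not homicidal ideation as such.

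So 3 of 5 conditions carry over and 5 − 3 = 2 do not.

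Could exclusion 15 be read as bringing in all of 8.2? Its opening words refer to contraindications to nortriptyline in general, but a colon and a specific list follow, with nothing to mark the items as examples. Exclusions 16 and 17, for local anaesthetics and topical oestrogen, are left open with no list. The contrast favours reading 15 as the listed items only.

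Could exclusion 1 fill the gap? It concerns drugs, not diagnoses. It names gabapentin, which section 3.2 describes as an anti-epileptic, and pregabalin among drugs to be stopped before entry, and the list is open. A doctor reviewing the medications may well discover treated epilepsy, but the rule sets a washout and does not exclude the condition.

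Chance of exposure once randomised:

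- Inputs: four arms at 1:1:1:1 (5.3); nortriptyline in two of them (8.1); 400 women planned (section 2).
- Probability of nortriptyline = arms with the drug / all arms = 2/4 = 0.50.
- Across the trial, 400 × 0.50 = 200 women are allocated to it.

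The plan states no figure on this point, so there is none to reproduce. It also gives no prevalence of epilepsy, so the number of affected women cannot be derived.

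For the antidepressants, 8.9 and 8.2 conflict directly. The 8.2 consultation asks whether a woman on such drugs could safely take nortriptyline in this trial, and its 24-hour contact applies to randomised women still taking serotonergic antidepressants. Section 8.9 allows no SSRI or SNRI at any time in the study. Neither section says which prevails.

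**The case against.** The strongest reply is that the protection is already there. Section 8.2 is part of the protocol, sits under a risk-reduction heading, and 18.1 requires compliance with the whole document. The same section carries entry rules elsewhere: it says women sensitive to estradiol should not be enrolled. An investigator who randomised a woman with known epilepsy would be acting against 8.2. Exclusions 11 and 15 can also be read more broadly than above, and the medication review gives doctors a chance to stop her. All of this stands, and it lowers the severity. It does not remove the mismatch, because 5.3 ties randomisation to the criteria and a site working through 7.3 is not prompted to ask about epilepsy.

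A reader might infer that the protocol permits women with controlled epilepsy to enter. The documents do not support that: 7.3 fails to exclude them clearly, while 8.2 says they should not have the drug.

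A reader might also take the adverse event list, which includes seizures, as a sign that such women are expected. Section 14.2.1 explains the list otherwise: "The study is limiting collection of AEs to focus on potential impacts of the blinded study medication". Monitoring for a drug effect says nothing about who is admitted.

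Finally, a reader might see a wider failure in the many drugs on the Appendix C handout that neither 7.3 nor 8.9 names. How many entries go unnamed does not measure risk. Medications are documented and discussed at screening, and every participant receives the handout. A compulsory cross-check against it would be a preference rather than the repair of an error.

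**Conclusion.** The mismatch is real: two of the five conditions in 8.2 are missing from 7.3. Epilepsy is the one that matters in practice; homicidal ideation partly overlaps the psychosis and suicidality wording and is mainly a point of consistency. The only size the documents support is the 50% chance of nortriptyline for a woman who is randomised. It rests on equal allocation and on nobody having stopped her under 8.2 or during the medication review. Any estimate of how many women would be exposed needs an outside prevalence and an assumption about physician behaviour, and none is offered here.

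This should be fixed, but it falls short of a mandatory correction because the prohibition on use is already written in 8.2. Confidence is high that the terms are missing and much lower that an affected woman would actually enter. The conflict between 8.2 and 8.9 is a genuine inconsistency in its own right and adds no weight to the epilepsy point.

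**What to change.** Add epilepsy or seizure disorder, whether controlled or not, to exclusion 15, and add homicidal ideation so that the item matches 8.2. The cost is a short wording change and a few extra screen failures.

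Separately, state whether 8.9 or 8.2 governs SSRIs and SNRIs. If 8.9 governs, remove the consultation and 24-hour contact text from 8.2 so far as it concerns those drugs, and name them in 7.3. If 8.2 governs, amend 8.9 to allow them after the prescriber has been consulted. Either choice is a text edit. The first may reduce the eligible pool; the second keeps the calls to prescribers and participants that 8.2 already describes.
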